7.1 Investigational Agent – Ublituximab

Ublituximab is available as a sterile, clear to opalescent, preservative-free concentrate for solution for intravenous (IV) by infusion administration. It will be supplied at a concentration of 25 mg/mL in 6 mL (150 mg) single-use glass vials. The shelf life of ublituximab is 36 months if stored between +2°C / + 8°C based on stability data and should be stored in a secured, limited-access, refrigerated area at a temperature ranging from +2°C / + 8°C. Ublituximab must not be frozen. Ublituximab must not be mixed with other medicinal products during preparation and should only be diluted with 0.9% NaCl before use.

No incompatibility of ublituximab with PVC bags containing 0.9% NaCl or PVC tubing has been observed. Studies performed in both static and dynamic conditions, showed no significant loss of CD16 activity and no adsorption or degradation of the protein were noted. Ublituximab diluted in 0.9% NaCl is stable for 24 hours in static condition at 25°C and in dynamic conditions it is stable for 8 hours at 25°C.

Diluted ublituximab should be checked before administration for cloudiness, color, or deposits. Ublituximab should not be administered if does not conform to the specifications. Immediately inform TG Therapeutics, Inc. at [contact] with any product quality concerns or questions.

It is recommended that ublituximab be administered immediately after dilution. It should NOT be mixed the day before and mixing should only occur once confirmed that patient is eligible for therapy on the day of treatment.

No live vaccines can be administered within 4 weeks of the initial dose of ublituximab or while receiving ublituximab.

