2.4.4 Ublituximab Clinical Pharmacokinetics/Pharmacodynamics

Ublituximab has been investigated in 10 sponsored clinical trials in patients with relapsed and refractory hematologic malignancies. Pharmacokinetics (PK) of ublituximab has been determined in subjects with relapsed or refractory CLL in a dose escalation Phase I study. Main PK findings demonstrated intrasubject variability for ublituximab serum concentrations over different time points and at all dose levels ranging from 10%-220%. Exposure appeared to increase more than dose proportionally with increasing dose over the tested ranges. Clearance after single and repeated infusion decreased with increasing dose thereby increasing terminal

half-life. Lastly upon additional dosing of 4 weekly doses of 450mg resulted in higher serum concentrations at Day 50 indicating accumulation of free ublituximab in serum is maintained after seven successive infusions.

Significant lymphocyte depletion was observed in all subjects reflecting the intended biological activity ublituximab. Lymphocyte depletion was maximal after the 4th dose with median depletion of 97% relative change persisting for one month. After 8 weekly doses lymphocyte depletion was unchanged but persisted for over 6 months after the last dose.

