2.5 Risk/Benefit Assessment

Overall, the data from non-clinical studies in non-human species have not revealed any potentially serious toxicities that would preclude the use of umbralisib in patients with hematologic malignancies. Further, data from the ongoing studies of umbralisib has not revealed any unexpected safety trends, and umbralisib has been well tolerated up through 1200 mg QD of the micronized formulation, with patients now on umbralisib for durations in excess of four-years; however long term safety data is only available from a limited number of patients, and should therefore be cautiously extrapolated to other target populations. Considering the clinical activity demonstrated by the class of PI3K δ inhibitors to date, along with the preliminary activity demonstrated by umbralisib thus far, in conjunction with manageable safety profile, the potential benefit-risk ratio of umbralisib is anticipated to be positive in patients with hematologic malignancies. Upon the administration of ublituximab to subjects with CD20-positive lymphoproliferative disorders, one should be aware of the AEs reported in the safety data from the completed and ongoing Phase I studies with ublituximab and the known side-effects reported thus far with other anti-CD20 monoclonal antibodies.

Preliminary safety profile of ublituximab has been inferred from two Phase I studies in advanced stage subjects with CLL and lymphoma exposed to 4 to 8 weekly infusions of the product, and from a limited number of B-Cell Lymphoma subjects exposed to ublituximab in combination with other anti-cancer agents for longer durations. It should therefore be cautiously extrapolated to other target populations and other schedules of ublituximab infusions and or combinations. Taking into account the above mentioned risks, special attention has to be focused on management of acute infusion-related reactions and monitoring of complete blood cell count in order to detect and treat if necessary early or late episodes of neutropenia. In conclusion, considering the more active pre-clinical profile of ublituximab compared with rituximab in B-cell lymphoproliferative disorders, the rapid, profound and sustained blood lymphocyte depletion, the interim assessment of response and the manageable toxicity observed in the Phase I and II studies, the potential benefit-risk ratio of ublituximab is anticipated to be positive in subjects with B-cell malignancies.

3. Subject Selection

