5.2. Treatment Administration

All treatment will be administered on an outpatient basis. See section 5.2.1 and 5.2.2 for special precautions relevant for each specific study agent administration. All therapy will be administered in cycles with each cycle consisting of 28 days.

Enrolled subjects will initiate umbralisib monotherapy for a one cycle lead-in defined by Cycle -1. This cycle is designed to allow for correlative assay sample collection to assess early clonal shifts after umbralisib therapy. Without the lead-in these shifts may otherwise be masked by peripheral elimination of circulating tumor cells by anti-CD20 therapy. Subjects will be monitored closely upon initiation with a C-1D15 visit to assess tolerability of umbralisib monotherapy. Upon completion of Cycle -1 subjects will then continue on daily umbralisib and initiate combination therapy with ublituximab (U2). Ublituximab administration and induction/continuation is defined in Section 5.2.1. Ublituximab will only be administered through Cycle 6 (i.e no maintenance administration). Starting at C7D1 enrolled subjects will continue on umbralisib monotherapy. Umbralisib will be given on a continuous once daily basis starting at Cycle -1 for each 28 cycle until disease progression, discontinuation due to toxicity, subject death, subject withdrawal of consent, or investigator withdrawal. Administration schedule and timing of umbralisib administration in relation to ublituximab are further defined in Section 5.2.3. The overall treatment administration is depicted in the schema below Figure 1.

Subjects will be evaluated for objective response after completion of 6 cycles of combination therapy. Subjects with a response \geq PR will be allowed to continue on study (umbralisib monotherapy maintenance). A subject that does not meet objective response criteria by IwCLL 2018 guidelines outlined in Section 9.1 at C7D1 must be taken off study. See section 5.4.1 for further details in management of these subjects not meeting strict response criteria after completion of combination therapy.

Figure 1. Study Drug Administration Schema

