5.2.1 Ublituximab

Ublituximab infusions will be administered as an outpatient and consistent with previous Phase II and Phase III dosing schemes. During Cycle 1, infusions will occur on Day 1, Day 2, Day 8, and Day 15. On days 1 and 2 the 900mg will be split, with each subject receiving 150mg on day 1 and the remaining 750mg on day 2. All subsequent infusions starting from Cycle 1 Day 8 will consist of a single 900mg infusion of ublituximab. After completion of Cycle 1, dosing of ublituximab will occur on a monthly basis (q28 days) on day 1 of Cycles 2-6 (+/- 3 days). Starting at Cycle 1 Day 1 through Cycle 6 Day 1 ublituximab infusions will be in combination with oral administration of umbralisib. After 6 cycles of combination treatment, ublituximab infusions will be stopped and subjects will continue on umbralisib monotherapy. Titration schedules should follow the schema depicted in the Table 2. Upon completing Cycle 6 ublituximab infusions will be completed and subjects will not receive maintenance ublituximab. Subjects will continue with umbralisib monotherapy as described in Section 5.2.3.

Subjects will be eligible to start a new cycle of combination therapy with ublituximab unless they are experiencing toxicity requiring treatment delay as outlined in Section 6.2 Table 4.

Ublituximab should not be administered as an IV push or bolus. All subjects must be premedicated before ublituximab infusion with an antihistamine (diphenhydramine 50mg or equivalent), and a corticosteroid (dexamethasone 20 mg or equivalent dose) as follows:

- If pre-medications are administered IV: start the ublituximab infusion 30 minutes after conclusion of the last pre-medication infusion. If IV premedications are given over longer than a 30 minute timeframe per institutional standards, begin ublituximab within 10 minutes of stop time of last pre-medication.
- If pre-medications are administered orally: start the ublituximab infusion 45-60 minutes after ingestion of the oral pre-medications
- Adjusting antihistamine and corticosteroid doses, adjusting the timing of administration and/or additional pre-medications may be used at investigator discretion for additional prophylaxis against infusion related reactions

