5.2.2 Management of Infusion Related Reactions

Since infusion-related hypotension may occur, antihypertensive medications should be held 12-24 hours prior to and throughout ublituximab infusion. Infusion related reactions including severe reactions have been reported with ublituximab administration in patients with CLL. Guidelines are provided below for patients who experience such reactions. Symptomatic infusion reactions, despite premedication, may be treated at the discretion of the treating physician, including but not limited to: oral acetaminophen 650 mg (or equivalent), corticosteroids, antihistamines, oxygen, and bronchodilators.

If an infusion related reaction is observed at any time during the ublituximab treatment, the treating investigator may reduce the infusion flow rate at their discretion.

The following are recommended infusion rate reduction/delay guidelines for patients who experience severe Infusion Related Reactions (IRR's) in which treatment should be interrupted. Final decision for infusion rate reduction/delay or discontinuation resides with the treating investigator.

1st or 2nd Infusion Interruption:

- Hold infusion and closely monitor patient, institute symptomatic medical management until resolution of IRR symptoms. Treating investigator must be notified by research team and documentation should occur in the patient chart.
 - Symptomatic medical management should include administration of acetaminophen, antihistamines, and/or corticosteroids for fever (temperature $>38^{\circ}\text{C}$) and/or chills
 - Physician may order meperidine for persistent rigors, caution to be exercised if

- patient is hypotensive and meperidine may contribute to ongoing hypotension.
- Administer antihistamines and/or corticosteroids for flushing, urticarial, pruritus, or angioedema
- Administer IV fluid boluses for hypotension
- Administer epinephrine, corticosteroids and antihistamines in the event of an anaphylactic reaction
- Following the judgment of the Investigator, and provided the patient is stable, the infusion may be resumed at half the previous rate.
- If the patient does not experience any further IRR symptoms, infusion rate escalation may resume at the increments and intervals as appropriate at the treatment cycle dose (see Section 5.2.1)
- For any Grade 4 infusion related reaction, ublituximab should be stopped indefinitely. Subjects that experience a Grade 4 infusion reaction will not be allowed to be rechallenged.

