5.2.3 Umbralisib

Umbralisib will be administered orally as four 200mg capsules taken once daily for a total daily dose of 800mg. Umbralisib should be taken within 30 minutes of starting a meal. All subjects will initiate a one cycle lead in prior to starting combination therapy with ublituximab, subjects will initiate taking umbralisib on Cycle -1 day 1 through Cycle -1 day 28. Starting on Cycle 1 day 1, subjects may take the dose of umbralisib before or after infusion with ublituximab but umbralisib must be taken within 30 minutes of starting a meal. Subjects will continue daily oral dosing of 800mg umbralisib for 28 days which will constitute a cycle. Subjects should try to take the drug at the same time each day throughout the trial. Subjects should be instructed to swallow the tablets whole and should not chew or crush them. If a dose of umbralisib is missed, it should be taken as soon as possible on the same day. If it is missed for a period of greater than 12 hours, it should be skipped for that day. If vomiting occurs, no attempt should be made to replace the vomited dose. Subjects will continue daily dosing of umbralisib until disease progression, toxicities, or study completion whichever comes first.

Subjects will be eligible to start a new cycle of either combination or monotherapy of umbralisib unless they are experiencing toxicity requiring treatment delay as outlined in Section 6.2 Table 4.

Umbralisib will be dispensed at the sites by the research coordinator or designee under the direction of the PI or by a pharmacist at the site. Before dispensing, the site pharmacist or authorized designee must check that the umbralisib is in accordance with the product specifications and the validity is within the re-test date. Immediately inform TG Therapeutics, Inc. at [contact] with any product quality concerns or questions.

Subjects must be provided drug in its original container. Subjects will be dispensed sufficient umbralisib for roughly 1 cycle of treatment. If the interval between visits is greater than 1 cycle, subjects may be given more than 1 cycle of umbralisib so that they do not have to return between scheduled visits. Subjects should be instructed to return all empty and partially filled bottles including any unused tablets when they return to the site. Study drug compliance should be reviewed with the subject at the beginning of each new treatment cycle and as needed.

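### The live-vaccine ban in Section 7.1 stops with ublituximab, between C6D1 and C7D1, although umbralisib continues and lymphocyte depletion may outlast the ban

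*Combined protocol and SAP*

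**What the plan says.** Section 7.1, on ublituximab, states: "No live vaccines can be administered within 4 weeks of the initial dose of ublituximab or while receiving ublituximab". Section 7.2 (umbralisib) and Section 5.3 (concomitant medication and supportive care) have no vaccine rule, and none appears elsewhere.

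On timing, Section 5.2.3 starts umbralisib one cycle before ublituximab: "subjects will initiate taking umbralisib on Cycle -1 day 1 through Cycle -1 day 28". Section 5.2.1 then says: "Starting at Cycle 1 Day 1 through Cycle 6 Day 1 ublituximab infusions will be in combination with oral administration of umbralisib". There is no ublituximab maintenance, and Section 5.2 continues: "Starting at C7D1 enrolled subjects will continue on umbralisib monotherapy". Section 5.4 plans at least 18 months of that monotherapy. Section 5.4.1 lets any subject start C7D1 and stay for up to 3 cycles while response is being assessed. Ublituximab can also end early; Section 5.2.2 says: "For any Grade 4 infusion related reaction, ublituximab should be stopped indefinitely".

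On how long the effect lasts, Section 2.4.4 gives two figures. The first is: "Lymphocyte depletion was maximal after the 4th dose with median depletion of 97% relative change persisting for one month". The second is: "After 8 weekly doses lymphocyte depletion was unchanged but persisted for over 6 months after the last dose". Of the ublituximab safety profile, Section 2.5 warns: "It should therefore be cautiously extrapolated to other target populations and other schedules of ublituximab infusions and or combinations".

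On infection precautions, Section 5.3 has PJP prophylaxis begin before umbralisib and asks for zoster prophylaxis in all subjects. The pneumonitis note in Table 4 (Section 6.2) makes both kinds of prophylaxis mandatory. Sections 5.1.2.6 and 5.1.2.7 schedule CMV PCR testing.

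**The concern.** A rule with a stated end can be read as permission once that end has passed. Here the end is tied to ublituximab dosing, not to how long its effect lasts or to whether the subject is still on study drug. A site following Section 7.1 literally could allow a live vaccine at or soon after C7D1. At that point the subject is taking a PI3K delta inhibitor under mandatory antimicrobial prophylaxis and may still be lymphocyte-depleted from ublituximab.

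Other parts of the protocol point to the same risk. Section 2.4.5 includes varicella among the Grade 3 or greater infections in the first-in-human ublituximab trial. Section 12.1.3 lists hypogammaglobulinaemia and decreased immunoglobulins among events at least possibly related to the combination. Prophylaxis and CMV testing lessen the concern but do not replace a vaccine rule.

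What is at stake is the safety of individual subjects. The response rate, its confidence interval and the sample size do not depend on this rule.

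**Working it through.** The plan gives no figure for time without a vaccine rule, so there is nothing to reproduce. The check is date arithmetic.

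**Inputs**
- Cycle length: 28 days (Section 5.2).
- Ublituximab, in days after C1D1 (Section 5.2.1): 0 and 1 (150 mg + 750 mg, one split dose), 7, 14, 28, 56, 84, 112, 140. That is 8 full 900 mg doses in 9 infusions.
- Depletion: one month after the fourth dose; more than six months after the last of eight weekly doses (Section 2.4.4).
- Month length: 365.25/12 = 30.44 days. This is an assumption; 28 to 31 days was also tried.

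**When the ban lapses**
- Last infusion, C6D1: 5 × 28 = day 140.
- End of the last combination cycle, C7D1: 6 × 28 = day 168.
- Which day applies depends on how the words about receiving ublituximab are read.

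**Depletion time with no rule**

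From C6D1 the gap is D, the persistence after the last dose in days. From C7D1 it is D − 28. Dividing by 28 gives cycles.

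| Persistence | D (days) | From C6D1 | From C7D1 |
|---|---|---|---|
| One month | 30.4 | 30.4 days (1.09 cycles) | 2.4 days (0.09 cycle) |
| Six months | 182.6 | 182.6 days (6.52 cycles) | 154.6 days (5.52 cycles) |

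The source says more than six months, so the second row is the minimum for that scenario. The documents give no upper limit.

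**Sensitivity, from C7D1**
- Months of 28 to 31 days: 0 to 3 days in the one-month case; 5.0 to 5.64 cycles in the six-month case.
- Visit windows (C6D1 infusion ±3 days, C7D1 ±5 days) put 20 to 36 days between the two visits: 0 to 0.37 cycle and 5.24 to 5.81 cycles.

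**Umbralisib time with no rule, whatever the depletion**
- Planned monotherapy: at least 18 × 30.44 = 548 days; 548/28 = 19.6 cycles.
- Any subject who starts C7D1: up to 3 × 28 = 84 days.

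**What supports each part of that period**
- Six months after C6D1 is day 140 + 182.6 = 322.6, about C12D15.
- Up to then the six-month depletion figure, if it carries over, supports a ban.
- For a subject who completes the planned monotherapy, the remaining 19.6 − 5.5 = 14.1 cycles rest mainly on precaution during umbralisib.

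**The case against.** The strongest objection is to the evidence. Neither depletion figure comes from this regimen. Here eight full doses are spread over 140 days with umbralisib, against four doses or eight weekly doses in Section 2.4.4. The only dose which that section names for a weekly schedule is 450 mg, against 900 mg here. Eight doses is the closer match by count, but the caution in Section 2.5 applies. For the same reason the one-month and six-month results are two scenarios from two regimens, not the ends of one interval. This stands, and the size has to be stated conditionally.

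The measure is also imperfect. In CLL the leukemic cells accumulate in the blood (Section 2.1), and a falling lymphocyte count is a response criterion (Section 9.1.2). Part of the reported depletion may be tumour clearance, and no section separates it from loss of normal immunity. Section 9.1.3 notes that umbralisib can raise the lymphocyte count, but as a disease measure, so it settles nothing about immunity either way. This stands too.

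A reader might infer that umbralisib itself rules out live vaccines. No section says so. Mandatory prophylaxis shows that the plan foresees infection risk; it is not a vaccine contraindication. The investigator brochures, cited for adverse events, are not available here and may give guidance. Extending the ban through monotherapy is therefore a precaution consistent with the plan's own measures.

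A reader might also infer that the ban starts too late, because four weeks before C1D1 is C-1D1, the first umbralisib day. The documents set no vaccine washout before umbralisib. Adding one could delay treatment by up to 28 days in subjects with progression and a treatment indication. That change is not supported.

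Finally, investigators may avoid live vaccines anyway. That lowers the likelihood of harm, but the protocol includes an explicit rule, and its stated end is what sites will read.

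**Conclusion.** The concern holds as a minor safety gap in a rule that ends too early. Section 7.1 stops restricting live vaccines between C6D1 and C7D1, or sooner in a subject who stops ublituximab early and stays on umbralisib. No other section takes over.

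If the depletion reported after eight weekly doses carries over, more than about 5.5 cycles from C7D1 (more than about 6.5 from C6D1) are left without a rule. If depletion lasts only about a month, the gap is about 2 days from C7D1, which is immaterial, or 30 days from C6D1. Umbralisib continues without a rule in either case. The figures assume the planned dosing dates and a 30.44-day month, and the longer one is an extrapolation using an imperfect proxy.

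A reader might take 5.5 cycles as the most that could be uncovered; the wording in Section 2.4.4 makes it the least for that scenario. A reader might also try to turn the gap into a number of subjects at risk. The documents do not say how many would be offered a live vaccine, and it could be none. The primary endpoint is unaffected.

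**What to change.** Replace the vaccine sentence in Section 7.1 with:

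*Live vaccines are not permitted in the 4 weeks before the first ublituximab dose, at any time during study treatment (including umbralisib monotherapy), or for at least 6 months after the last ublituximab dose.*

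The six months is a floor taken from Section 2.4.4. It also covers subjects who stop both drugs at or soon after C7D1 and those who stop ublituximab early. No interval after the last umbralisib dose is proposed, because the documents give no basis for one.

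The change needs one amended sentence and no added visits or tests. Its real cost is that some subjects wait longer for a live vaccine: at least six months after the last ublituximab dose, and at least the planned 18 months of monotherapy for those who stay on umbralisib.
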